### KCCQ physical limitation score

The KCCQ physical limitation score will be defined as

$100 \times$  the mean of the non-missing response scores among items {1(a)-1(f)},  
if there are at least three non-missing response scores among items {1(a)-1(f)}; the score will  
be left as missing if there are not enough non-missing response scores among these items.

### KCCQ symptom stability score

The KCCQ symptom stability score will be defined as

$100 \times$  the response score for item 2,  
if the response score for item 2 is non-missing; the score will be left as missing if the response  
score is missing.

### KCCQ symptom frequency score

The KCCQ symptom frequency score will be defined as

$100 \times$  the mean of the non-missing response scores among items {3, 5, 7, 9},

if there are at least two non-missing response scores among items {3, 5, 7, 9}; the score will be left as missing if there are not enough non-missing response scores among these items.

### **KCCQ symptom burden score**

The KCCQ symptom burden score will be defined as

$100 \times$  the mean of the non-missing response scores among items {4, 6, 8},  
if there are at least one non-missing response scores among items {4, 6, 8}; the score will be left as missing if the response scores are missing for all items among items {4, 6, 8}

### **KCCQ self-efficacy score**

The KCCQ self-efficacy score will be defined as

$100 \times$  the mean of the non-missing response scores among items {10, 11},  
if there are at least one non-missing response scores among items {10, 11}; the score will be left as missing if the response scores are missing for both item 10 and item 11.

### **KCCQ quality of life score**

The KCCQ quality of life score will be defined as

$100 \times$  the mean of the non-missing response scores among items {12, 13, 14},  
if there are at least one non-missing response scores among items {12, 13, 14}; the score will be left as missing if the response scores are missing for all items among items {12, 13, 14}.

### **KCCQ social limitation score**

The KCCQ social limitation score will be defined as

$100 \times$  the mean of the non-missing response scores among items {15(a)-15(d)},  
if there are at least two non-missing response scores among items {15(a)-15(d)}; the score will be left as missing if there are not enough non-missing response scores among these items.

**Table 2-7 KCCQ summary scores**

Summary Score	Relevant Items	Minimum Number of Non-Missing Response Scores
KCCQ physical limitation score	1(a)-1(f)	3
KCCQ symptom stability score	2	1
KCCQ symptom frequency score	3, 5, 7, 9	2
KCCQ symptom burden score	4, 6, 8	1
KCCQ self-efficacy score	10, 11	1
KCCQ quality of life score	12, 13, 14	1
KCCQ social limitation score	15(a)-15(d)	2

In summary, the above seven KCCQ summary scores will be defined as 100 times the mean of the non-missing response scores for the relevant items, if there are enough items with non-missing response scores among the relevant items. The relevant items and the minimum number of non-missing response scores are given in [Table 2-7](#).

**KCCQ total symptom score**

The KCCQ total symptom score will be defined as the mean of the non-missing scores among the KCCQ symptom frequency score and the KCCQ symptom burden score. The KCCQ total symptom score will be left as missing, if the KCCQ symptom frequency score and the KCCQ symptom burden score are both missing.

**KCCQ clinical summary score (CSS)**

The KCCQ CSS will be defined as the mean of the non-missing scores among the following.

- KCCQ physical limitation score
- KCCQ total symptom score

If the above scores are both missing, the KCCQ CSS will be left as missing.

**KCCQ overall summary score (OSS)**

The KCCQ OSS will be defined as the mean of the non-missing scores among the following.

- KCCQ physical limitation score
- KCCQ total symptom score
- KCCQ quality of life score
- KCCQ social limitation score

If the above scores are all missing, the KCCQ OSS will be left as missing.

**2.6.1.1 KCCQ clinical summary score (CSS) change from baseline**

For patients who have died, the KCCQ CSS after the death will be imputed as zero.

For patients who permanently discontinue study treatment, values collected after permanent discontinuation will generally be included in the analysis.

The changes from baseline in KCCQ CSS will be analyzed using a MMRM model, in which, the response variable will be the changes from baseline in KCCQ CSS; stratum (ACEi, ARB, No RASi), region, treatment (LCZ696, IMT), visit and treatment-by-visit interaction will be included as fixed-effect factors; baseline KCCQ CSS (BCSS), BSBP, stratum-by-BCSS, stratum-by-BSBP, and visit-by-BCSS interactions will be included as covariates; the within-patient covariance will be modeled using an unstructured covariance matrix (a common matrix for the two treatment groups). If the model fitting procedure does not converge, the AR(1) covariance structure will be used. The analysis will include all post-baseline scheduled visits up to Week 24 (Week 4, Week 12, Week 16 and Week 24) and will be performed based on the likelihood method with an assumption of MAR for missing data (other than due to death).

Based on the MMRM model, the secondary null hypothesis,  $H_3$ , will be tested (if applicable) based on the testing strategy, the estimates and the two-sided 95% confidence intervals will be provided for the adjusted mean changes from baseline in KCCQ CSS at each post-baseline scheduled visit (Week 4, Week 12, Week 16 and Week 24) in both treatment groups (LCZ696 and IMT), and for the adjusted mean difference (LCZ696 minus IMT) at each post-baseline scheduled visit (Week 4, Week 12, Week 16 and Week 24). The corresponding one-sided p-values will also be provided based on the MMRM model.

In addition, the improvement and the deterioration in KCCQ CSS will be analyzed separately, to further illustrate the clinical relevance of the observed differences in terms of proportion of responders, using longitudinal binary logistic regression models, in which, the response variables will be, the KCCQ CSS improvement (event defined by at least 5-points improvement in KCCQ CSS) and the KCCQ CSS deterioration (event defined by at least 5-points deterioration in KCCQ CSS), accordingly; stratum (ACEi, ARB, No RASi), region, treatment (LCZ696, IMT), visit and treatment-by-visit interaction will be included as fixed-effect factors; BCSS, BSBP, stratum-by-BCSS, stratum-by-BSBP and visit-by-BCSS interactions will be included as covariates; patient-specific intercepts will be included as random effects. The analysis will include all post-baseline scheduled visits up to Week 24 (Week 4, Week 12, Week 16 and Week 24) and will be performed based on the likelihood method with an assumption of MAR for missing data (other than due to death). No multiplicity adjustment will be done for these supportive responder analyses (i.e., the tests for the responder analyses will be performed at nominal level of one-sided 0.025).

Based on the longitudinal binary logistic regression models, the estimates and the two-sided 95% confidence intervals will be provided for the adjusted odds ratios (LCZ696 / IMT) at each post-baseline scheduled visit (Week 4, Week 12, Week 16 and Week 24). The corresponding one-sided p-values will also be provided based on the longitudinal binary logistic model.

Besides, the KCCQ CSS and the change from baseline in KCCQ CSS will be summarized by treatment group and visit, for overall and for each stratum (ACEi, ARB, No RASi), using number of observations, mean, standard deviation, median, minimum, Q1, Q3, and maximum; the improvement and the deterioration in KCCQ CSS of at least 5-points will be summarized by treatment group and visit, for overall and for each stratum (ACEi, ARB, No RASi), using the numbers and percentages of patients whose KCCQ CSS improved at least 5 points, whose KCCQ CSS deteriorated at least 5 points, whose KCCQ CSS changed less than 5 points, and whose KCCQ CSS is missing.

As additional supportive analyses, the Mantel-Haenszel estimates and the corresponding 95% confidence intervals will be provided by visit, for the relative risks and the risk differences, for KCCQ CSS improvement and KCCQ CSS deterioration, accordingly.

The FAS will be used for the above analyses.

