9.4.2 Statistical model, hypothesis, and method of analysis

Testing strategy

The following primary null hypotheses will be included in the testing strategy.

- H_1 : LCZ696 is no better than the comparator in change from baseline in log(NT-proBNP) at Week 12 in the overall study population
- H_2 : LCZ696 is no better than the comparator in change from baseline in 6MWD at Week 24 in patients with B6MWD ranging from 100 meters to 450 meters.

The following secondary null hypotheses will be included in the testing strategy.

- H_3 : LCZ696 is no better than the comparator in change from baseline in KCCQ CSS at Week 24 in the overall study population.
- H_4 : LCZ696 is no better than the comparator in NYHA change from baseline at Week 24 in the overall study population.

Each null hypothesis is tested against the one-sided alternative that LCZ696 is better than the comparator in the corresponding variable.

In order to control the family-wise type-I error rate at the one-sided 0.025 significance level, a sequentially rejective multiple testing procedure based on the graphical presentation ([Bretz et al 2009](#)) will be employed, whereby H_1 and H_2 will be tested first at initially assigned level of one-sided $(9/10) \times \alpha = 0.0225$ and one-sided $(1/10) \times \alpha = 0.0025$, accordingly. If H_1 and/or H_2 are rejected, the alpha for the rejected null hypotheses will be propagated to H_3 , such that, H_3

[figure not shown]
will be tested at the updated alpha level (one-sided 0.025 if both H_1 and H_2 are rejected; one-sided 0.0225 if H_1 is rejected but H_2 is not rejected; one-sided 0.0025 if H_2 is rejected but H_1 is not rejected); if H_3 is rejected, the alpha will be propagated to H_2 or H_4 based on the initial step rejection status.

- With H_1 rejected but H_2 not rejected at the initial step, if H_3 is rejected at one-sided 0.0225, the alpha will be propagated to H_2 , such that, H_2 will be tested again at one-sided 0.025; if H_2 is rejected at one-sided 0.025, the alpha will be further propagated to H_4 . Otherwise, the testing procedure will stop.
- With H_2 rejected but H_1 not rejected at the initial step, if H_3 is rejected at one-sided 0.0025, the alpha will be propagated to H_4 , such that, H_4 will be tested at one-sided 0.0025. Otherwise, the testing procedure will stop.

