- With both H_1 and H_2 rejected at the initial step, if H_3 is rejected at one-sided 0.025, the alpha will be propagated to H_4 , such that, H_4 will be tested at full alpha (one-sided 0.025). Otherwise, the testing procedure will stop.

Figure 9-1 provides graphical illustration of the sequentially rejective testing procedure.

Figure 9-1 Graphical illustration of the sequentially rejective testing procedure

Based on the above testing procedure, if applicable, H₁, H₂ and H₃ will be tested based on the corresponding MMRM models (Section 9.4.2, Section 9.5.1.1), H₄ will be tested based on the longitudinal proportional cumulative odds model (Section 9.5.1.3)

If statistical significance had been established in the mean difference in change from baseline to Week 24 for KCCQ CSS, the following responders will be analyzed accordingly, based on the longitudinal binary logistic regression models (Section 9.5.1.1), to further illustrate the clinical relevance of the observed differences in terms of proportion of responders.

- KCCQ CSS improvement (defined by at least 5 points improvement);
- KCCQ CSS deterioration (defined by at least 5 points deterioration);

No multiplicity adjustment will be done for these supportive responder analyses (i.e., the tests for the responder analyses will be performed at nominal level of one-sided 0.025).

NT-proBNP analyses

The changes from baseline in log(NT-proBNP) will be analyzed using a mixed model for repeated measures (MMRM), in which, the response variable will be the changes from baseline in log(NT-proBNP); stratum (defined by prior ACEi/ARB medication usage [ACEi, ARB, None]), region, treatment (LCZ696, individualized medical therapy), visit and treatment-by-visit interaction will be included as fixed-effect factors; baseline log(NT-proBNP), stratum-by-baseline and visit-by-baseline interactions will be included as covariates; the within-patient covariance will be modeled using an unstructured covariance matrix (a common matrix for the two treatment groups). The analysis will include all post-baseline scheduled visits up to Week 12 (Week 4, Week 12) and will be performed based on the likelihood method with an assumption of missing at random (MAR) for missing data (Siddiqui et al 2009, National Research Council 2010).

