### 3 Sample size calculation

The sample size (2500 randomized patients) has been chosen in order to provide adequate power to evaluate both primary and secondary endpoints.

With an alpha of one-sided 0.0225, the power for the NT-proBNP will range from 92% to more than 99%, to detect a relative reduction ranging from 11% to 24% in change from baseline to Week 12 in NT-proBNP, assuming a standard deviation of 0.81 for change from baseline in the log-transformed NT-proBNP (based on PARAMOUNT-HF data of patients with baseline KCCQ CSS < 75) and an overall drop-out rate of 10%.

With an alpha of one-sided 0.0025, the power for the 6MWD will range from 90% to 99%, to detect a mean difference ranging from 22 meters to 30 meters in change from baseline to Week 24 in 6MWD, assuming a standard deviation of 120 meters ([Ingle et al 2005](#)), an overall drop-out rate of 10%, and an overall proportion of 88% for patients with B6MWD ranging from 100 meters to 450 meters.

With an alpha of one-sided 0.0225, the power for the KCCQ CSS will range from 87% to 99%, to detect a mean difference ranging from 2 points to 3 points in change from baseline to Week 24 in KCCQ CSS, assuming a standard deviation of 15.52 points for change from baseline in the KCCQ CSS (based on PARAMOUNT-HF data of patients with baseline KCCQ CSS < 75) and an overall drop-out rate of 5%.

All alpha levels in the following sample size calculations will be one-sided 0.025.

This sample size of 2500 randomized patients aims to provide a power of approximately 90%, with the one-sided alpha level of 0.025, to demonstrate a 5% responder advantage in at least 5-point deterioration for patients who are treated with LCZ696 over IMT when assuming the proportion of patients with at least 5-point deterioration from baseline to Week 24 in the IMT group is 20% (based on PARAMOUNT-HF data of patients with baseline KCCQ CSS < 75) and an overall 5% dropouts.

With the same assumption of the dropout rate, this sample size will also provide a power of 69% to detect a 5% responder advantage in at least 5-points improvement in the KCCQ clinical summary score for patients who are treated with LCZ696 over IMT when assuming the proportion of patients with at least 5-points improvement from baseline to Week 24 in the IMT group is 55% (based on PARAMOUNT-HF data of patients with baseline KCCQ CSS < 75).

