## 4 Change to protocol specified analyses

No change from protocol.

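### The SAP omits the protocol's condition that KCCQ CSS responder tests follow only a significant KCCQ CSS mean difference, while stating that nothing changed

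*SAP*

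**What the plan says.** **Protocol.** Section 9.4.2 sets out the graph for H1 to H4, whose purpose is stated as "In order to control the family-wise type-I error rate at the one-sided 0.025 significance level". It then turns to the two KCCQ CSS responder endpoints and opens that paragraph with a condition: "If statistical significance had been established in the mean difference in change from baseline to Week 24 for KCCQ CSS". Only after that condition does it waive multiplicity adjustment and set a nominal one-sided level of 0.025. The synopsis has the same wording. Section 9.5.1.1 describes the responder models without repeating the condition, but promises only odds ratios with 95% confidence intervals at Week 24, not a test or a p-value.

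**SAP.** Section 2.5.2 reproduces the H1 to H4 strategy and leaves out the responder paragraph. Section 2.6.1.1 gives the purpose of the responder analyses as "to further illustrate the clinical relevance of the observed differences in terms of proportion of responders, using longitudinal binary logistic regression models". It adds "No multiplicity adjustment will be done for these supportive responder analyses", explains that "the tests for the responder analyses will be performed at nominal level of one-sided 0.025", and says of Weeks 4, 12, 16 and 24: "The corresponding one-sided p-values will also be provided based on the longitudinal binary logistic model". No section of the SAP states the condition. Section 4 reads in full: "No change from protocol".

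**The concern.** The two responder proportions are listed secondary endpoints in both documents, with their own power statements and sensitivity tables. They are outside the graph and carry no alpha, so the condition on H3 is the only thing that limits when a nominal p-value for them can be produced.

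As the SAP is written, the responder tests are run and their p-values reported in two situations that protocol 9.4.2 excludes: when H3 is tested and not rejected, and when neither H1 nor H2 is rejected, so that H3 is never tested. A report could then show a nominally significant proportion of responders with no established mean difference behind it. That defeats the stated purpose, which is to illustrate a difference already shown.

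**Working it through.** **1. The texts side by side.**

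| Item | Protocol 9.4.2 and synopsis | Protocol 9.5.1.1 | SAP 2.5.2 and 2.6.1.1 |
|---|---|---|---|
| Condition on KCCQ CSS mean | Yes | Not repeated | Absent |
| Responder tests | Nominal one-sided 0.025, if condition met | None stated | Nominal one-sided 0.025 |
| Output | Tests | Week 24 odds ratio and 95% CI | Odds ratio, 95% CI and one-sided p-value at four visits |

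Two endpoints at four visits give 2 × 4 = 8 unconditional p-values. The SAP does write conditions where it means them: for H3 (2.6.1.1) and H4 (2.6.2) it says the test is made only if applicable under the strategy. The responder paragraph has no such qualifier.

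**2. Inputs** (protocol 9.8, SAP section 3): 2500 randomized 1:1; 5% dropout; SD of KCCQ CSS change 15.52; control rates 20% (deterioration) and 55% (improvement); responder level one-sided 0.025; H3 level 0.0225 for power. Per arm, n = 2500 × 0.95 / 2 = 1187.5.

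**3. The plan's own figures reproduce.** For two proportions, power = Φ{[Δ − 1.960 √(2p̄(1−p̄)/n)] / √[(p₀(1−p₀) + p₁(1−p₁))/n]}.
- 20% v 15%: (0.05 − 0.0306) / 0.01556 = 1.249, power 89.4% (stated: about 90%).
- 55% v 60%: (0.05 − 0.0398) / 0.02026 = 0.505, power 69.3% (stated: 69%).
- KCCQ mean at 0.0225: SE = 15.52 √(2/1187.5) = 0.637. For 2 points, Φ(3.140 − 2.005) = 87.2%; for 3 points, Φ(4.710 − 2.005) = 99.7% (stated: 87% to 99%).

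The power figures are sound; the problem is only the missing condition.

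**4. Chance of a nominal responder result at Week 24 with no true effect.** Assume normal changes with SD 15.52 and a mean change of 6.95 in both arms, which gives 55% improved and 22% deteriorated, close to the plan's rates. The test statistics then have these correlations: mean with improvement 0.80, mean with (reversed) deterioration 0.71, and the two responder statistics with each other 0.59.
- Without the condition: P(either) = 0.025 + 0.025 − P(both) = 0.050 − 0.006 = 0.044. For reference, independent tests would give 1 − 0.975² = 0.0494, and the Bonferroni bound is 0.050.
- With the condition, H3 at 0.0225: P(either, and H3 rejected) = 0.014.
- Difference: 0.044 − 0.014 = 0.030, all of it arising when H3 is not rejected.

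Mean changes of 0 and 5 points give 4.4% against 1.4% to 1.5%. Simulating whole trials gave 4.4% to 4.6% against 1.4% to 1.6%.

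**5. Limits.** With the condition, the null rate cannot exceed the H3 level, which is at most 0.025, whatever the model. If neither H1 nor H2 is rejected, the conditional rate is zero.

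**The case against.** Several points on the other side have weight.

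- **No confirmatory error rate is touched.** A reader might infer that the SAP inflates the family-wise error. It does not. The responder tests are outside the graph in both documents, are called supportive, and use a level described as nominal. About 4.4% is the ordinary result of two correlated 0.025 tests.
- **The protocol does not forbid the analyses.** A reader might infer that no responder analysis may be run unless H3 succeeds. Protocol 9.5.1.1 and the endpoint table commit to responder results without a condition. What the protocol makes conditional is the testing.
- **The condition may be inherited.** The SAP says it implements protocol v02, and section 4 could mean that the condition still holds. The documents do not show a deliberate removal. But the SAP directs that tests and p-values be produced regardless of H3, so inheritance by silence does not settle what is programmed.
- **Results under a true benefit are not false positives.** If a 1-point true difference is assumed, about 9% of trials would miss H3 and still show a nominal responder result. That is not a type I error and should not be counted as harm.
- **The remedy is partly labelling.** A 95% interval excluding 1 in the favourable direction carries the same information as one-sided p < 0.025. The gain is that no significance statement is made.
- **Ungated p-values are usual in this SAP.** It also gives them for 6MWD, NYHA and SF-36 PCS responders. Only the KCCQ CSS responders had a protocol condition to lose.

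**Conclusion.** The discrepancy stands in limited form. On the testing of the KCCQ CSS responder endpoints, SAP 2.5.2 and 2.6.1.1 do not carry the condition in protocol 9.4.2 and the synopsis, and the statement in SAP section 4 is inaccurate on this point. H1 to H4 remain controlled at one-sided 0.025.

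Under no true effect, the chance of at least one nominally significant Week 24 responder result is about 4.4% to 4.5% as the SAP is written and about 1.4% with the condition. These figures are illustrative. They assume normal changes, crude two-proportion tests at a single time point and H3 tested at 0.0225. The planned model is a covariate-adjusted longitudinal logistic model with random intercepts, and deaths are scored zero. The textual finding does not depend on them. It should be corrected before database lock, but it does not threaten the primary conclusions.

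**What to change.** In SAP 2.5.2 and 2.6.1.1, state that the KCCQ CSS responder tests are performed only if H3 is rejected under the testing strategy. Otherwise, report the odds ratios and 95% confidence intervals as descriptive, with no p-values or significance statement. This agrees with protocol 9.4.2 and 9.5.1.1 read together.

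If dropping the condition was intended, declare it in SAP section 4 with a reason, and label the responder p-values descriptive whenever H3 is not rejected.

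Either route costs a sentence or two in the SAP and matching table footnotes before database lock. Design, data collection and sample size do not change.

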#### **2.6.1.2 KCCQ overall summary score (OSS) change from baseline**

As additional exploratory analyses, the same analyses as KCCQ CSS will also be performed for KCCQ OSS, except that the BCSS in the analysis models will be replaced by baseline KCCQ OSS (BOSS), stratum-by-BCSS and visit-by-BCSS interactions in the analysis models will be replaced by stratum-by-BOSS and visit-by-BOSS interactions.

The FAS will be used for the above analyses.

